The primary objective of this study is to compare the proportion of patients who develop major bleeding episodes (WHO grades 3-4) in the group randomized to receive prophylactic EACA versus standard of care prophylactic platelet transfusions.

2.2 Secondary Objectives:

- To compare the proportion of patients who develop any bleeding episode in the group randomized to receive prophylactic EACA versus standard of care prophylactic platelet transfusions.
- To compare, according to treatment with prophylactic EACA or prophylactic platelet transfusions, the total number of units of platelet transfused
- To compare the quality of life in both arms of the study

2.3 Hypothesis:

This is a non-inferiority trial in which we hypothesize that in thrombocytopenic patients with hematological malignancies, comparable incidence of bleeding will be observed with the prophylactic use of EACA and standard of care arm prophylactic platelet transfusions.

3 Investigational Plan

3.1 Overall Study Design and Plan:

This is a single center, randomized phase 2, open label trial of oral EACA versus platelet transfusions for the prevention of bleeding in thrombocytopenic patients with hematological malignancies.

Eligible patients with acute or chronic thrombocytopenia will be randomized in a 1:1 fashion to receive oral EACA at the dose of 1,000 mg twice daily as a substitute for prophylactic platelet transfusions or standard of care prophylactic platelet transfusions for an untransfused platelet count $< 20 \times 10^9/L$ in the out-patient or in the in-patient setting. Patients will be assessed twice weekly and as needed in between visits for the presence of bleeding. The number of platelets transfused for prophylaxis (arm B) or for therapeutic purposes (both arms) will be monitored. Patients will complete quality of life questionnaire. Adverse events will be assessed and graded according to the National Cancer Institute Common Terminology Criteria for Adverse Events (CTCAE) version 4.0. Bleeding will be assessed and graded according to the World Health Organization (WHO) classification [Appendix 1]. Patients will be assessed according to a protocol-specific schedule of events. Patients will continue treatment on trial until one or more criteria for discontinuation are met. Patients will be supplied with study drug until they discontinue from the study. Patients will be followed for 2 years or death, whichever occurs first.

3.2. Primary Endpoint:

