5.1 Schedule of Events

Table 3. Screening and study procedures to be done through the end of the study. Evaluation visit samples or activities should occur within 3 days of the scheduled study day

	Screening	Cycle 1					Monthly (until Month 6)	End of treatment
	Day <21	Day 1	Day 8 ±3days	Day 15 ±3days	Day 22 ±3days	Day 1 ±3days		
Informed Consent	X							
History and Demographics	X							
Hematological disorder diagnosis and prior therapy	X							
Urine HCG	X							
Vital Signs, ECOG PS and Physical Examination	X	X	X	X	X	X	X	
Concomitant medications	X	X	X	X	X	X	X	

Randomization	X						
CBC*	X	X	X	X	X	X	X
Fibrinogen	X						
Comprehensive metabolic panel**	X	X	X	X	X	X	X
Patient's questionnaire QOL		X					X
Transfusions records		X	X	X	X	X	X
Diary card***		X	X	X	X	X	X
Bleeding score WHO*	X	X	X	X	X	X	X
AE's		X	X	X	X	X	X
SAE		X	X	X	X	X	X

*First 30 days , i.e.: twice weekly or at the discretion of the treating physician, but at least once a week.(If the decision is twice a week, the non-visit day bleeding score may be assessed in person or by phone). After 30 days CBC and bleeding score will be performed according to the standard of care for cytopenic patients **glucose, serum calcium, blood urea nitrogen, creatinine, sodium, potassium, chloride, serum albumin, serum total proteins, carbon dioxide, alkaline phosphatase, aspartate amino transferase and alanine amino transferase. The screening procedures including blood and urine test obtained as part of the routine care, up to 72 hours prior to consenting, may be used to qualify the subject for eligibility and randomization. *** Diary card to be completed by Arm B - EACA

The following describes the procedures/tests required for this study:

Informed Consent: All patients must take part in the informed consent process prior to any study related activity. During the consent process, the person obtaining consent must inform the patient of all elements of informed consent. Adequate time must be allowed for questions and for the patient to make a voluntary decision. No protocol-specific procedures are to be performed until the patient has signed and dated the IRB approved informed consent form. Each patient's participation in the trial begins with the signing and dating of the informed consent form.

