Bleeding score: Bleeding will be graded according with the WHO bleeding scale (Appendix 1) and recorded in the medical records during each visit. For hospitalized subjects enrolled on this trial, bleeding will be described in the daily follow up note by physician, nurse practitioner or physician assistant and graded by the investigator.

End of Treatment or Early Termination Procedures: The End-of-Treatment (or early termination) Visit should be performed within 2 weeks (14 days) of the patient's last dose of study drug or the patient/investigator decision to end treatment, whichever is later.

Follow-up Procedures: Safety: All AEs ongoing or starting within 30 days after the End-of-Treatment must be recorded on the CRF. After this time, ongoing AEs thought to be at least possibly study-drug related and all ongoing SAEs should be followed at least every 4 weeks until they resolve to baseline (or CTCAE grade ≤ 1), stabilize, or are considered to be chronic or irreversible.

Follow-up Procedures: Survival: Survival data will be collected every 12 weeks \pm 2 weeks starting after the last dose of the assigned study treatment or the investigator/patient decision to discontinue treatment, whichever occurs later and continuing for up to 12 months from the time the last patient is randomized to a treatment group. These data do not need to be obtained during a visit; phone contact is acceptable.

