5.2.2 Early Discontinuation

In the event that a patient is withdrawn from the study, every effort will be made by the Investigator to document and report the reasons for withdrawal as thoroughly as possible. The reason(s) for termination must be clearly reported on the appropriate page of the patient's CRF. An End-of-Treatment reason for discontinuation must be recorded for any patient who is randomized. If a patient is discontinued from the trial for any reason, every effort must be made to perform all clinical and laboratory procedures as scheduled for the End-of-Treatment Visit. In the event that the patient fails to return for the necessary visit(s), an effort must be made to contact the patient to determine the reason, and this information should be recorded in the appropriate source record and the end-of-treatment CRF.

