5.4 Withdrawal Criteria

- Patients will be discontinued from further study drug administration if any of the following occur:
Intolerable toxicity as determined by the Investigator
- Grade 4 bleeding on either arm of this study
- Development on trial of a deep venous thrombosis, pulmonary embolism or cerebrovascular event on either arm of this study
- Grade ≥ 2 CPK elevation on the EACA arm
- Grade ≥ 3 myalgia on the EACA arm
- Development on trial of disseminated intravascular coagulation (DIC)
- Development on trial of a condition that requires anticoagulation
- A treatment interruption for study-drug (EACA) related non-hematologic toxicities lasting longer than 28 days
- Significant deviation from the protocol or eligibility criteria
- Noncompliance with study or follow-up procedures
- Pregnancy
- Patient withdrawal of consent and decision to discontinue participation
- Termination of the trial
- Any other reason that, in the opinion of the Investigator, would justify removal of the patient from the study

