6.3.2 Dose Escalation

Patients randomized to EACA who experience any persistent grade ≥ 2 bleeding including hematuria, will receive platelet transfusions as per standard of care and have the option of increasing the dose of EACA to 1,000 mg three times a day. If the dose of 1,000 mg TID is poorly tolerated, then the EACA will be held and restarted at 1,000 mg BID after resolution of the AEs to $<$ grade 1.

If patient experience oral bleeding secondary to acute or chronic gingivitis or mucositis who do not respond to chlorhexidine 0.12% oral rinse and antibiotic treatment (including but not limited to penicillin and metronidazole or amoxicillin and clavulanate or ampicillin and sulbactam or clindamycin), then have the option of increasing the dose of EACA to 1,000 mg three times a day. If the dose of 1,000 mg TID is poorly tolerated, then the EACA will be held and restarted at 1,000 mg BID after resolution of the AEs to $<$ grade 1.

Patients randomized to EACA who have persistent cutaneous bruises will receive platelet transfusions as per standard of care and have the option of increasing the dose of EACA to 1,000 mg three times a day. If the dose of 1,000 mg TID is poorly tolerated, then the EACA will be held and restarted at 1,000 mg BID after resolution of the AEs to $<$ grade 1. If bruising continues, patient will be taken off study.

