8.5.2 Primary Endpoint Analysis

The primary analysis of the primary endpoint will be performed using a one-sided fisher exact test to compare the proportions of patients with major bleeding during the whole study between the two arms. The significance level is set at 0.05. This primary analysis will be based on the ITT population.

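### Section 6.3.2 takes only EACA patients off study for continuing bruising, and no bleeding score is scheduled after the exit visit, so later major bleeds can go unrecorded in one arm; the effect is probably small but not bounded by the protocol

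*Protocol*

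**What the plan says.** - **Exit rule (Protocol 6.3.2).** EACA patients with persistent bruises receive platelets and may go to three-times-daily dosing; then "If bruising continues, patient will be taken off study". The two preceding paragraphs, on other bleeding, end with dose adjustment and contain no removal. Section 5.4 has no bruising exit for the platelet arm.
- **Other EACA-only stops (5.4).** CPK elevation, myalgia, and "A treatment interruption for study-drug (EACA) related non-hematologic toxicities lasting longer than 28 days".
- **Primary analysis (8.5.2).** A one-sided Fisher test in the ITT population, to "compare the proportions of patients with major bleeding during the whole study between the two arms".
- **Bleeding assessment (5.1, Table 3).** The row "Bleeding score WHO" runs from screening to the End of treatment column, which is the last column. That visit is due within 14 days of the last dose or of the decision to stop, whichever is later.
- **After early discontinuation (5.2.2).** "every effort must be made to perform all clinical and laboratory procedures as scheduled for the End-of-Treatment Visit". No later bleeding assessment is named.
- **After the exit visit (5.1).** "All AEs ongoing or starting within 30 days after the End-of-Treatment must be recorded on the CRF". Ongoing SAEs and possibly related AEs are then followed, and "Survival data will be collected every 12 weeks", by phone if need be.
- **Long-term follow-up (3.1, 5.3).** Section 3.1 says "Patients will be followed for 2 years or death, whichever occurs first". Neither section schedules a bleeding score in that period.

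**The concern.** The endpoint is counted over the whole study in all randomized patients, but scoring stops when treatment stops. One of the reasons for stopping exists in one arm only and is itself a sign of bleeding. A control with the same bruises goes on being scored until platelet recovery or month 6, unless an exit common to both arms intervenes.

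If a removed EACA patient with no recorded major bleed is counted as a non-event, the missing bleeds favour EACA. An SAP can choose how to handle such a patient, but it cannot recover bleeds that were never collected. At stake is a modest bias in the primary comparison of an unblinded trial. The platelets given in the same paragraph of 6.3.2 are not the problem.

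**Working it through.** **1. The plan's own figure.** Section 8.4 gives 45 per arm for 80% power with a one-sided Fisher test at 5%, 8% versus 30%. Exact enumeration gives 80.05% at 45 per arm, and 45/0.90 = 50. The design figure reproduces.

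**2. Length of the gap.** Section 8.1 sets a month at 28 days, so month 6 is day 6 × 28 = 168. After a decision to stop on day d, a new bleed is picked up until day d + 14 + 30 = d + 44 at the latest. With d = 28 (assumption), capture ends by day 72 and up to 168 − 72 = 96 days are uncovered, or fewer if platelets recover.

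**3. How many patients.** In the 44-patient EACA series (Table 2) there were 4 skin-bruise episodes, all grade 1 and none needing platelets. Nobody stopped EACA for bruising. The one-sided 95% upper bound for 0/44 is 1 − 0.05^(1/44) = 6.6%, and 50 × 0.0658 = 3.3. I therefore take 0 to 3 removals, with 4 and 5 as stress values. That series did not operate the removal rule, so it is only a guide.

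**4. Effect on the test.** Inputs: 50 per arm; both arms truly at 30% (the planned control rate); reject if the one-sided Fisher p < 0.043 (final level in 8.8); interim looks ignored. Let m be the number removed and r their major-bleed risk after exit. Controls are Bin(50, 0.30).

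- All later bleeds missed, counted as non-events: EACA events are Bin(50 − m, (15 − m·r)/(50 − m)), denominator 50. With r = 0.30 the probability stays 0.30. With r = 0.60 and m = 3 it is (15 − 1.8)/47 = 0.281.
- Half caught, r = 0.30: Bin(50 − m, 0.30) + Bin(m, 0.15), denominator 50.
- Removed patients excluded, r = 0.30: Bin(50 − m, 0.30), denominator 50 − m.

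One-sided false-positive rate:

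| m removed | all missed, r = 0.30 | half caught, r = 0.30 | excluded, r = 0.30 | all missed, r = 0.60 |
|---|---|---|---|---|
| 0 | 2.7% | 2.7% | 2.7% | 2.7% |
| 1 | 3.1% | 2.9% | 2.6% | 3.6% |
| 2 | 3.6% | 3.1% | 2.7% | 4.8% |
| 3 | 4.1% | 3.4% | 2.7% | 6.2% |
| 4 (stress) | 4.7% | 3.6% | 2.5% | 8.0% |
| 5 (stress) | 5.4% | 3.9% | 2.6% | 10.2% |

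The r = 0.60 column is an assumption: the protocol gives no risk for patients with continuing bruising.

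**5. Effect on the estimate.** The expected understatement of the EACA proportion is m·r/50. At r = 0.30 that is 0.6 percentage points per removed patient and 1.8 points for three. At r = 0.60 it is 1.2 and 3.6 points. These are expected values, not maxima: one bleed actually missed moves the proportion by 1/50 = 2 points.

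**The case against.** **Off study may only mean off EACA.** Possibly, but scoring still ends at the End-of-Treatment visit, so the gap is the same on either reading.

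**AE recording already captures these bleeds.** In part. WHO grade 3 includes any bleed needing red cells, so a major bleed within 30 days of the exit visit is unlikely to escape the CRF. AEs are graded by CTCAE rather than WHO, however, and a new bleed after that window has no scheduled capture. The half-caught column allows for this.

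**The rule may never be used, and the level holds.** This largely stands. None of the 44 patients stopped for bruising, and with 0 to 3 removals at average risk no rate exceeds 4.3%. Putting the whole 30% risk after exit is also severe, because part of the risk period has been observed by then.

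**Handling of early exits belongs in the SAP.** Agreed, and the direction of bias depends on it: excluding removed patients at average risk leaves 2.6-2.7%. The missing data collection is a protocol matter.

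**Controls can leave early too.** True. Grade 4 bleeding, thrombosis and investigator judgement apply in both arms. The asymmetry is limited to bruising and the EACA-only criteria, and the latter are not quantified here.

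**A stronger reading.** A reader might infer that the type I error is inflated or that the primary comparison is biased towards EACA. The documents do not support that. It would need more removals, or a higher risk in those removed, than anything they show, together with a non-event rule that the protocol does not state. Nor do they say that removed patients leave the ITT set.

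**Conclusion.** The protocol as written allows an arm-specific loss of primary-endpoint data, triggered by a bleeding sign, and this conflicts with a whole-study ITT comparison. The likely effect is small: a false-positive rate of 2.7-4.1% against 4.3% with 0 to 3 of 50 removed, even if every later bleed is missed and counted as a non-event.

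That conclusion rests on three assumptions: an exit rate no higher than the pilot series suggests, average 30% risk in those removed, and both arms truly at 30%. The documents fix neither the exit rate nor the risk after exit, so small is a judgement and not a bound. At twice the risk, three removals give 6.2%, above both 0.043 and 0.05. This is an inexpensive improvement worth making, not a flaw that undermines the trial.

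**What to change.** Replace the last sentence of the bruising paragraph in 6.3.2 with:

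> If bruising continues, EACA is stopped and the patient is treated per standard of care. The patient stays on study with WHO bleeding scores on the Table 3 schedule until platelet recovery as in 5.3 or month 6, and major bleeds in this period count in the ITT primary analysis.

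Add a sentence to 5.4 applying the same continued scoring, in both arms, to every early stop except withdrawal of consent or trial termination. Align Table 3 and the End-of-Treatment and follow-up text in 5.1, which now end scoring at that visit. Report how many patients have already been removed for bruising. No platelet regimen after stopping EACA needs to be prescribed.

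The cost is these text edits and a few more bleeding assessments. After day 30 these follow standard of care anyway, and Table 3 already allows phone scores on non-visit days in the first 30 days. The downside is that the EACA arm will include bleeds after the change of treatment, so the contrast is between strategies, as ITT already implies. The sample size does not change.

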6.3.3 Dose Reduction

Patients randomized to EACA 1000 mg twice a day or higher who experience grade ≥ 2 toxicity attributable to EACA, will hold the study drug until resolution of the adverse event to $<$ grade 1. EACA will then be reduced by 50%, restarted at 1000 mg daily after the resolution of the AE's to $<$ grade 1

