6.3.1 Dose Selection, Treatment Administration and Compliance

6.3.1.1 EACA

The starting dose of EACA will be 1,000 mg taken orally twice daily. Patients will take the prescribed number of tablets at approximately the same time each day. Patients will be provided a diary card where the date of administration will be recorded. Patients who forget to take their dose more than 6 hours after it is due shall not make up the missed dose. Any missing doses should be recorded, and subsequent training of patients should be documented in the appropriate source record (e.g., clinic chart). The starting dose was selected based on our institutional experience (Section 1.3).

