8.2 Analysis Population

Intention to treat (ITT) population: The ITT population includes all patients who are randomized to the study. Patients will be analyzed according to the treatment to which they were assigned.

Safety Population: The safety population includes all patients who have received at least 1 dose of EACA. Patients included in the safety population will be analyzed according to the treatment they received.

Per-protocol Population: The per-protocol population includes all patients who are randomized, receive at least one dose of study drug, and have no major protocol violations that could be expected to impact response data, such as: failure to satisfy one or more eligibility criteria, administration of other anti-cancer therapy concurrent with study drug, and administration of incorrect study drug doses. Major protocol violations will be finalized and documented prior to final data analysis.

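### Restart dose after EACA toxicity on the three-times-daily dose is inconsistent between Protocol sections 6.3.2 and 6.3.3, and within 6.3.3

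*Protocol*

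**What the plan says.** - **Starting dose (Protocol 6.3.1.1).** "The starting dose of EACA will be 1,000 mg taken orally twice daily".
- **Escalation (6.3.2).** Patients with persistent bleeding of grade 2 or higher, with oral bleeding that does not respond to local and antibiotic treatment, or with persistent bruising "have the option of increasing the dose of EACA to 1,000 mg three times a day". Each of the three paragraphs then gives the same step back: "If the dose of 1,000 mg TID is poorly tolerated, then the EACA will be held and restarted at 1,000 mg BID", once the adverse events have fallen below grade 1.
- **Reduction (6.3.3).** This section opens with "Patients randomized to EACA 1000 mg twice a day or higher who experience grade" 2 or higher toxicity attributable to EACA. The drug is again held until the event is below grade 1, and then "EACA will then be reduced by 50%, restarted at 1000 mg daily after the resolution of the AE's".
- **Discontinuation (5.4).** Some toxicities end study drug, so no restart dose arises. Examples are CPK elevation of grade 2 or higher, myalgia of grade 3 or higher, thromboembolic events, DIC, intolerable toxicity, and an interruption of more than 28 days for EACA-related non-hematologic toxicity.
- **Per-protocol population (8.2).** Examples of major violations that can remove a patient include "administration of other anti-cancer therapy concurrent with study drug, and administration of incorrect study drug doses".

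**The concern.** Sections 6.3.2 and 6.3.3 both tell staff what to do when a patient on the three-times-daily dose has drug toxicity. Both hold the drug to the same resolution criterion, but they resume it at different doses. Section 6.3.3 also gives two expressions for its own restart dose that do not match for such a patient.

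Two things are at stake. First, patients with the same toxicity could be restarted on different doses according to which sentence is read. This would happen when drug-attributable harm has already occurred and a single instruction is most needed. Second, the protocol treats dose correctness as a matter of compliance: incorrect dosing is a listed example of a major violation (8.2), and deviations are to be listed by treatment group (8.9). For these patients, a restart dose that follows one sentence departs from another.

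**Working it through.** **Inputs**
- Starting dose (6.3.1.1): 2 × 1,000 = 2,000 mg/day.
- Escalated dose (6.3.2): 3 × 1,000 = 3,000 mg/day.
- Tablet strength (6.5.3.1): 500 mg.

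**Step 1. Reproduce the plan's own figure.** From the twice-daily dose, 0.5 × 2,000 = 1,000 mg/day. This matches the milligram figure in 6.3.3, so for a patient who never escalated the rule is consistent.

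**Step 2. Does 6.3.3 reach the escalated dose?** Every EACA patient starts on the twice-daily dose, and the only higher dose in the protocol is the three-times-daily dose in 6.3.2. The extension of 6.3.3 to higher doses can therefore mean only escalated patients.

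**Step 3. Apply each instruction from 3,000 mg/day.**

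| Instruction | Restart dose | Cut from 3,000 mg/day | 500 mg tablets per day |
|---|---|---|---|
| 6.3.2, back to twice daily | 2,000 mg/day | 1 − 2,000/3,000 = 33.3% | 4 |
| 6.3.3, percentage | 0.5 × 3,000 = 1,500 mg/day | 50.0% | 3 |
| 6.3.3, milligram figure | 1,000 mg/day | 1 − 1,000/3,000 = 66.7% | 2 |

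The highest and lowest differ by a factor of 2,000/1,000 = 2. All three are whole numbers of tablets, so tablet strength rules none of them out.

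**Step 4. Can the triggers be told apart?** Section 6.3.2 is triggered by poor tolerance, which the protocol does not define. Section 6.3.3 is triggered by attributable toxicity of grade 2 or higher. An attributable grade 2 event on the three-times-daily dose can meet both descriptions, and no text gives either section precedence. Even if the triggers were treated as separate, the mismatch inside 6.3.3 (1,500 against 1,000 mg/day) would remain.

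**Step 5. Who is affected?** A patient must have been randomized to EACA, taken the optional escalation, then had attributable toxicity of grade 2 or higher, met no discontinuation rule in 5.4, and recovered enough to restart. The protocol gives no expected rate for these steps. The 44-patient preliminary series (1.3) used the twice-daily dose, so it says nothing about toxicity after escalation.

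**Step 6. Does it reach the analyses?** The primary analysis (8.5.2) and the secondary analyses (8.5.3) use the intention-to-treat population. The protocol assigns no analysis to the per-protocol population. The sample-size calculation (8.4) uses no dosing input.

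**The case against.** The best defence is that the two sections serve different purposes: 6.3.2 undoes an escalation that did not suit the patient, and 6.3.3 handles formal toxicity. On that reading only two doses are actually written, 1,000 mg twice daily and 1,000 mg daily; the 1,500 mg figure is derived from the percentage. It is true that 1,500 mg is never printed and that the triggers are worded differently. But the protocol does not separate them. The percentage is an explicit instruction in a sentence that extends to doses above twice daily, and it cannot be set aside without an amendment.

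A reader might infer more than the document supports, in three ways:

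- **That EACA dosing in general is undefined.** It is not. The starting dose, the escalated dose and the restart after toxicity on the twice-daily dose are each clear. Only the restart after toxicity on the three-times-daily dose is in doubt.
- **That every escalated patient with toxicity of grade 2 or higher is affected.** Section 6.3.3 requires the toxicity to be attributable to EACA, and section 5.4 takes several such patients off study drug altogether.
- **That the per-protocol population is undefined.** Section 8.2 defines it, limits exclusions to violations that could be expected to affect response data, and has violations settled before the final analysis. The uncertainty about incorrect dosing concerns this subgroup only.

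**Conclusion.** The contradiction stands, in limited form. For a patient on 3,000 mg/day with EACA-attributable toxicity of grade 2 or higher and no discontinuation rule met, the current text supports restart at 2,000, 1,500 or 1,000 mg/day. The count of three rests on two readings: that such an event can also count as poor tolerance under 6.3.2, and that the percentage in 6.3.3 applies to the dose the patient is then taking. Without the first, two doses still conflict inside 6.3.3. Without the second, 6.3.2 and the milligram figure still conflict wherever both triggers are met.

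The consequence is that staff could treat like patients differently, and that for this subgroup a breach of the dosing rules cannot be judged consistently. It does not follow that the trial's main comparison is compromised: the planned efficacy comparisons are by intention to treat, and neither they nor the sample size depends on this rule. The number of patients concerned cannot be computed from the protocol. The point should be corrected because it concerns dosing at the time of toxicity and costs little to put right, not because a planned result turns on it.

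**What to change.** Reconcile 6.3.2 and 6.3.3 in an amendment so that:

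1. each dose at onset of toxicity leads to exactly one restart instruction;
2. the text states which section governs when both triggers are met, or defines poor tolerance so that the triggers no longer overlap;
3. the percentage and the milligram figure in 6.3.3 agree for every dose the section covers.

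Removing only the percentage or only the milligram figure would not be enough, because the conflict between 6.3.2 and 6.3.3 would remain. If any patient has already been restarted after toxicity on the escalated dose, record before the final analysis how that restart is classified under 8.2. Which dose is right is for the investigators, and none is proposed here. The cost is amendment wording, with no change to sample size, endpoints or analyses.
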